- Change in the Sequential Organ Failure Assessment (SOFA) Score 48 hours, 72 hours and 7 days after randomization

Time schedule and study duration

The planned study duration is five months, being three months of recruitment, one month of follow up and one month for data analysis and manuscript writing. The first patient was enrolled on April 17th. The final report and publication are expected to be available on the second half of 2020.

Eligibility criteria

We will include critically ill patients with ARDS due to confirmed or probable COVID-19 admitted to the ICU. Probable COVID-19 is defined by the presence of symptoms, which are contemplated in the inclusion criteria, travel or residence in a city where community transmission is reported or contact with a confirmed case in the last 14 days prior symptoms onset⁽¹⁹⁾ and radiological imaging findings compatible with COVID-19 at the time of inclusion.

After 182 patients have been enrolled, the Steering Committee suggested specific changes on both inclusion and exclusion criteria. The timing of ARDS diagnosis for inclusion changed from 24 hours to 48 hours. The rationale for this modification was due to most centers receiving patients intubated in the ICU already with ARDS diagnosis and more than 24 hours of mechanical ventilation, which shortened the time window for recruitment. Additionally, given the widespread use of corticosteroids before ICU admission in Brazil, we allowed inclusion of patients who have previously received one day of corticosteroids during hospital stay, which was not allowed at first. The exclusion criteria were refined by adding three more criteria: use of immunosuppressive drugs, cytotoxic chemotherapy in the past 21 days, and neutropenia due to hematological or solid malignancies with bone marrow invasion.

Each patient must fulfil all the following inclusion criteria to be eligible for enrolment:

- Age ≥ 18 years old
- Probable or confirmed infection by SARS-CoV2
- Intubated and mechanically ventilated
- Moderate or severe ARDS according to Berlin criteria⁽²⁰⁾ (Table 2)

- Onset of moderate or severe ARDS in less than 48 hours before randomization

Exclusion criteria are:

- Pregnancy or active lactation
- Known history of dexamethasone allergy
- Daily use of corticosteroids in the past 15 days
- Indication for corticosteroids use for other clinical conditions (e.g refractory septic shock)

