Adherence to protocol and corticosteroids use in both groups is accessed daily. The use of corticosteroids in the control group is not forbidden since critically ill patients might have another

indication for corticosteroid use during their ICU stay. However, any use of corticosteroids for treating ARDS and or refractory hypoxemia in the control group is considered protocol deviation. Changes in dosage of dexamethasone or early interruption in the intervention group will also be considered protocol deviation.

If during the trial the patient is deemed to not have COVID-19 infection, which is defined by a negative laboratory tests along with negative evaluation by the Adjudication Committee, the study drug will be stopped, data on these patients will be collected until day 28 and will be included in the final analysis. However, giving the epidemiological context and inclusion criteria, it is expected that only a minority of patients will be in this group.

All centers will receive an initial training session before initiating recruitment to ensure consistency of the study procedures and data collection.

Data collection and management

Unidentified patient data will be collected through an electronic online data capture tool (REDCap).^(22,23) Demographic and baseline data, height, Simplified Acute Physiology Score (SAPS) 3, use of corticosteroids prior the randomization, and the HScore for diagnosis of secondary hemophagocytic lymphohistiocytosis (Table 3) are collected for all patients. The SOFA score is collected on days 1, 2, 3 and 7. Data from gas exchange, lung mechanics, hemodynamic, laboratory data, use of neuromuscular blocking agents, prone positioning and use of ECMO are collected prior randomization and until day 14.

The use of mechanical ventilation or any other ventilation/oxygen support (high flow nasal cannula, non-invasive ventilation, use of supplementary oxygen) and data on the 6-point Ordinal Scale (Table 1) are collected daily until day 28 or until hospital discharge whichever comes first. Vital status at ICU and hospital discharge and any other relevant clinical data such as nosocomial infections, insulin use for glycemic control, antibiotic use, and other therapies for COVID-19 (hydroxychloroquine, chloroquine and azithromycin) are collected.

Data on mechanical ventilation are collected in specific forms with data on date and time of initiation and discontinuation of therapy.

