Two interim analyses are planned for safety and efficacy evaluation, after 96 patients and 234 patients with the complete follow up to the primary outcome. Based on the results of these interim analyses, the DMC will decide if there is proof beyond a reasonable doubt that the intervention is effective or not safe in this population. The stopping rule for safety will be a p-value $<$ 0.01 and for efficacy p-value $<$ 0.001 (Haybittle–Peto boundary). The Haybittle–Peto boundary is a conservative stopping rule at interim analysis that has minimal impact in increasing type I error in two-arm trials.⁽²⁸⁾ The interim analyses will be performed by an external and independent DMC.

Statistical methods

Main analyses will follow the intention-to-treat principle. For the primary outcome, a generalized linear model will be built with beta-binomial distribution or zero/one inflated beta distribution, with center as random effect and adjusted for age, corticosteroid use before randomization and PaO₂/FiO₂ ratio. The effect size will be estimated as mean difference, the respective 95% confidence interval, and hypothesis testing. Missing data on the primary outcome will be dealt with using multiple imputation techniques.

For details regarding the analysis of the secondary outcomes and other analysis, please refer to the Statistical Analysis Plan (SAP) on the appendix 3 of the supplementary material.

The significance level for all analyses will be 0.05. There will be no adjustment for multiple testing. All analyses will be performed using the R software⁽²⁹⁾ (R Core Team, Vienna, Austria, 2020).

Subgroup and sensitivity analyses

We plan to perform subgroup analysis for the primary endpoint, including interaction parameters in the main model to:

- Age (< 60 and \geq 60)
- PaO₂/FiO₂ ratio (\leq 100 and > 100)
- SAPS3 (< 50 and \geq 50)
- Duration of symptoms at randomization, days (\leq 7 and > 7)
- Duration of moderate / severe ARDS to randomization, hours (\leq 24 hours and > 24 hours to 48 hours)
- Position at randomization; (prone or supine)
- HScore⁽³⁰⁾ (\geq 169 and < 169)
- Use of corticosteroids before randomization
- Use of vasopressors at randomization

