We will use the Haybittle–Peto boundary stopping rule for both safety and efficacy based on the evidence of significant differences between intervention or control group regarding ventilator free days at day 28, mortality or adverse events. The stopping rule for safety will be a p-value <0.01 and for efficacy p-value <0.001 . The Haybittle–Peto boundary is a conservative stopping rule at interim analysis that has minimal impact in increasing type I error in two-arm trials⁵. We will not adjust the final tests for sequential analysis. The interim analyses will be performed by an external and independent DMC.

Basic reporting principles:

The baseline characteristics of the patients will be displayed as the supplementary table 1 (**Table 1S**):

Table 1S - Baseline characteristics of included patients

	Dexamethasone (Dex.) n = xxx	Control (Cont.) n = xxx
Age, mean (SD)	xx.x ± xx.x	xx.x ± xx.x
Female sex, N (%)	xx.x (xx.x)	xx.x (xx.x)
SAPS3 score, mean (SD)	xx.x (xx.x)	xx.x (xx.x)
Number of non-pulmonary organ failures, median [IQR]	x.xx [x.xx - x.xx]	x.xx [x.xx - x.xx]
Time since onset of symptoms, median [IQR], days	x.xx [x.xx - x.xx]	x.xx [x.xx - x.xx]
Days intubated prior to randomization, median [IQR]	x.xx [x.xx - x.xx]	x.xx [x.xx - x.xx]
COVID-19, N (%)		
Positive	xx.x (xx.x)	xx.x (xx.x)
Negative	xx.x (xx.x)	xx.x (xx.x)
In analysis	xx.x (xx.x)	xx.x (xx.x)
Not collected/unavailable	xx.x (xx.x)	xx.x (xx.x)
Comorbidities, N (%)		
Hypertension	xx.x (xx.x)	xx.x (xx.x)
Diabetes	xx.x (xx.x)	xx.x (xx.x)
Former smoker	xx.x (xx.x)	xx.x (xx.x)
Active smoker	xx.x (xx.x)	xx.x (xx.x)
Obesity	xx.x (xx.x)	xx.x (xx.x)
Solid tumor	xx.x (xx.x)	xx.x (xx.x)
Hematologic malignancy	xx.x (xx.x)	xx.x (xx.x)
Heart failure	xx.x (xx.x)	xx.x (xx.x)
COPD	xx.x (xx.x)	xx.x (xx.x)
AIDS	xx.x (xx.x)	xx.x (xx.x)
Chronic renal failure	xx.x (xx.x)	xx.x (xx.x)
Chronic dialysis	xx.x (xx.x)	xx.x (xx.x)
Cirrhosis	xx.x (xx.x)	xx.x (xx.x)
Asthma	xx.x (xx.x)	xx.x (xx.x)
Neuromuscular disease	xx.x (xx.x)	xx.x (xx.x)
Previous MI	xx.x (xx.x)	xx.x (xx.x)
Clinical characteristics		
Systolic BP, mmHg, mean (SD)	xx.x ± xx.x	xx.x ± xx.x
Diastolic BP, mmHg, mean (SD)	xx.x ± xx.x	xx.x ± xx.x
HR, bpm, mean (SD)	xx.x ± xx.x	xx.x ± xx.x
SpO ₂ , %, mean (SD)	xx.x ± xx.x	xx.x ± xx.x
HScore ≥169, N ₀ (%)	xx.x (xx.x)	xx.x (xx.x)
Respiratory measures (mean, SD)		
PaO ₂ /FiO ₂	xx.x ± xx.x	xx.x ± xx.x
Tidal volume, mL/kg predicted body weight	xx.x ± xx.x	xx.x ± xx.x

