The primary objective is to evaluate the effectiveness of early intravenous (IV) dexamethasone administration in ventilator-free days at 28 days after randomization, defined as alive and free from mechanical ventilation in adult patients with moderate or severe ARDS due to confirmed or probable SARS-CoV2 infection. Patients discharged from the hospital alive before 28 days will be considered alive and free from mechanical ventilation at day 28. Number of days free from mechanical ventilation will be presented as mean and standard deviation. The treatment effect will be presented as mean difference, with 95% confidence interval and P-value. We will use a generalized linear model with beta-binomial distribution or zero/one inflated beta distribution, with center as random effect and adjusted for age, corticosteroid use before randomization and PaO₂/FiO₂ ratio.

All-cause mortality rates at 28 days will be analyzed using a mixed Cox model, with centers as random effects (frailty model). The treatment effect on SOFA Score 48h, 72h, and 7 days after randomization will be analyzed by a linear mixed model with centers as random effects. For the clinical status of patients, an ordinal logistic regression will be used. The results will be presented as a proportional odds ratio comparing two combinations: Intervention versus Control. The probability ratios will be derived from a mixed logistic regression of proportional probabilities adjusted for age and PaO₂/FiO₂ ratio, with random intercepts for the center. The cumulative ordinal scores will be presented separately, as well as the main secondary results. Each odds ratio will be estimated using mixed logistic regression. The same models will be used to compare the effects of treatment on the follow-up. In case of the proportional odds assumption is not met, categories of the Ordinal scale 1-4 will be grouped as a single category for the analysis. All secondary outcomes are exploratory and no adjustment for multiple testing will be made.

Adverse events will be expressed as counts and percentages and compared between groups using the Chi-square test. The main results will be displayed as the supplementary table 2 (**Table 2S**). The significance level for all analyses will be 0.05. There will be no adjustment for multiple testing. All analyses will be performed using the R software⁶ (R Core Team, Vienna, Austria, 2020).

Table 2S - Main results presentation

Outcomes	Dex.	Cont.	Treatment effect	

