Membership and size of the DMC	Membership will consist of three members, which include at least one clinician experienced in the clinical area and at least one experienced clinical statistician. Additional members experienced in clinical trials should reflect the other specialities involved in the trial. The DMC will be formed only by overseas members. The members should not be involved with the trial in any other way nor have competing interests that could impact on the trial. Any competing interests, both real and potential, must be declared. Although members may be able to act objectively despite such connections, complete disclosure enhances credibility. A short competing interest form should be completed and returned by the DMC members to the trial coordinating team (agreement and potential competing interests form). The members of the IDMC for this trial are: (1) [name] (Chair)

	
(2) [name] (Statistician)
 
(3) [name]

The Chair, how they are chosen and the Chair's role	
The Chair should have previous experience of serving on DMCs and experience of chairing meetings and be able to facilitate and summarize discussions. The Chair will be chosen by the Academic Steering Committee and will be responsible for choosing the other two DMC members. The Chair is expected to facilitate and summarize discussions and keep copies of all reports and communications.
 
Other Chair's roles are:
 
 1. Hold all DMC meetings and ensure that all relevant data is reviewed 2. Ensure that only DMC members are present during the analysis and deliberation of the DMC data 3. Approve written minutes of all closed sessions of the DMC meetings 4. Create and archive written minutes of all executive sessions of DMC meetings. These minutes will remain confidential only to DMC members until after the database has been blocked and the sponsor's disclosure. 5. Arrange additional consultations with subject matter experts as needed.
The responsibilities of the DMC statistician	
The DMC statistician will be chosen by the DMC Chair and will provide independent statistical expertise. The statistician appointed by the DMC Chair will perform independent statistical analyses and have unlimited access to the entire study database. However, the analysis plan of the independent statistician of the DMC should follow the same principles described in the statistical analysis plan of the study.

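### Cheap efficiency gain, not an error: the 28-day mortality Cox model leaves out age and PaO₂/FiO₂, which the neighbouring models adjust for

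*Combined protocol and SAP*

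**What the plan says.** For 28-day mortality, the SAP (Appendix 3) says: "All-cause mortality rates at 28 days will be analyzed using a mixed Cox model, with centers as random effects (frailty model". The DMC charter (Appendix 4, primary outcome and all-cause mortality analysis) specifies the same model, again without patient-level covariates. The protocol's Statistical methods section refers secondary outcomes to the SAP and adds none.

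The neighbouring models differ. The primary model is "adjusted for age, corticosteroid use before randomization" and PaO₂/FiO₂. The ordinal model for clinical status at day 15 is adjusted for age and PaO₂/FiO₂. No reason is given for treating mortality differently.

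The covariates are available. Data collection and management lists "Demographic and baseline data, height, Simplified Acute Physiology Score (SAPS) 3, use of corticosteroids prior the randomization" for all patients, and gas-exchange data "are collected prior randomization and until day 14". All three covariates are in Table 1S.

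The SAP calls all secondary outcomes exploratory. Mortality also enters the interim stopping rule, which looks for differences "regarding ventilator free days at day 28, mortality or adverse events". The charter adds that "the analysis plan of the independent statistician of the DMC should follow the same principles described in the statistical analysis plan of the study".

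**The concern.** When a baseline variable predicts death, a Cox model that includes it usually tests treatment with more power than one that omits it. The plan has already named two such variables for the ordinal model, so using them for mortality needs no new data and leaves no room for choosing covariates after the fact. As written, death within the day-15 ordinal analysis appears to be adjusted while death at day 28 is not.

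What is at stake is power for an outcome that clinicians will read closely. To a lesser degree it is also the sensitivity of the interim harm rule, since the charter carries the SAP's approach into the DMC analyses.

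**Working it through.** **The plan's own figures.** The only sample-size calculation is for ventilator-free days. Per arm, n = 2(1.96 + 0.8416)² × 9² / 3² = 141.3, so 142 and 284 in total (286 with the t distribution), against the stated 290. Then 290 × 1.15 × 1.04 = 346.8, against the stated 350. Both agree within 3%. No death rate, hazard ratio or power is given for mortality.

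**Inputs.** From the documents: N = 350, 1:1 allocation in blocks of 2 and 4 within centre, 51 centres, 28-day follow-up, the eligibility change after 182 patients, and looks at 96 and 234. Assumed: control mortality, hazard ratio (HR), covariate strength, centre frailty SD 0.3, and prior corticosteroids in 30% of the last 350 − 182 = 168 patients (about 50, or 14% overall).

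**Starting power without covariates.** Schoenfeld's formula: events D = 175 × [p + 1 − (1 − p)^HR], power = Φ(√(D/4) × |ln HR| − 1.96).

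- p = 40%, HR 0.70: D = 122.6, power 50.6%
- p = 65%, HR 0.70: D = 204.8, power 72.3%
- p = 40%, HR 0.80: D = 128.7, power 24.4%
- p = 65%, HR 0.80: D = 213.2, power 37.0%

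Power is well short of its ceiling, so extra efficiency is useful.

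**Simulated gain.** 1,500 trials per setting, exponential survival censored at day 28, Cox model with a fitted Gaussian centre effect, Wald test at 0.05. Log-HR per SD of age / per SD of PaO₂/FiO₂ / for prior corticosteroids: weak 0.2/0.1/0.1 (c-index 0.55), moderate 0.4/0.2/0.2 (0.61), strong 0.8/0.3/0.2 (0.70). Power in %, unadjusted to adjusted:

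| HR, control mortality | Weak | Moderate | Strong |
|---|---|---|---|
| 0.70, 40% | 46.5 to 47.3 (+0.8) | 46.4 to 50.3 (+3.9) | 39.4 to 51.2 (+11.8) |
| 0.70, 65% | 68.5 to 70.1 (+1.6) | 67.2 to 73.1 (+5.9) | 53.7 to 72.9 (+19.2) |
| 0.80, 40% | 23.5 to 23.7 (+0.2) | 19.9 to 21.5 (+1.6) | 17.8 to 23.1 (+5.3) |
| 0.80, 65% | 35.1 to 35.7 (+0.6) | 29.7 to 34.9 (+5.2) | 25.5 to 36.3 (+10.8) |

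Simulation error of the paired differences is 0.5 to 1.2 points, so the weak gains are hard to tell from zero. Prior corticosteroids contribute −0.3 to +0.7 points beyond age and PaO₂/FiO₂, so the gain comes from those two. Type I error is 4.6 to 5.1% unadjusted and 4.5 to 5.1% adjusted.

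**Second simulation, separate code and inputs** (control mortality 40 or 55%, HR 0.65 or 0.75). Gains are +0.6 to +2.1 at c about 0.58, +1.2 to +3.8 at c about 0.61, and +2.1 to +6.6 at c about 0.63. With centre frailty fitted (control mortality 50%, HR 0.70, c about 0.63), power goes from 52.7 to 58.1%. Type I error is 4.5% unadjusted and 4.8% adjusted.

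**Where the gain comes from.** A conditional HR of 0.70 appears as 0.71 to 0.75 without covariates. The hazard ratio is non-collapsible, so adjustment moves the target further from 1; it does not remove a bias.

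**Missing PaO₂/FiO₂** (HR 0.70, mortality 50%, moderate; age and PaO₂/FiO₂ in the model). Unadjusted 53.5%, adjusted with full data 58.3%: a gain of 4.8. Complete-case power with 5 / 10 / 20% missing is 55.0 / 52.2 / 47.9%; with mean imputation it is 58.3 / 58.4 / 58.2%. At 5% missing, 55.0 − 53.5 = 1.5 points remain. As a rough check, 58.3% corresponds to a shift of 2.170; multiplied by √0.95 it is 2.115, giving 56.1%, and by √0.90 it is 2.058, giving 53.9%. So about 5% complete-case loss removes much of the gain, and about 10% removes essentially all of it.

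**Interim harm rule** (p < 0.01; assumed HR 1.5, control mortality 45%, moderate). Chance of crossing: 9.8 to 10.8% at 96 patients, 29.9 to 33.9% at 234.

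**The case against.** The best case against is that this is a preference. The unadjusted model is valid, the outcome is exploratory, and every input that sets the gain is assumed. Eligibility admits only PaO₂/FiO₂ of 200 or below, which narrows that covariate's range, so weak prognostic strength is at least as arguable as moderate. The simulated models are also correctly specified, which favours adjustment. All of this stands, and it is why the weak band belongs beside the moderate one.

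The loss is also partly covered. The day-15 ordinal analysis, which includes an alive-versus-dead split, is adjusted, and the adjusted primary outcome scores death by day 28 as zero. That reduces what is lost but does not supply an adjusted 28-day hazard ratio. Interim relevance is limited too: the second look may be cancelled, and the DMC may weigh factors outside the thresholds.

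The objection is right that copying the primary model's full covariate set is unnecessary. On prior corticosteroids the protocol says "we allowed inclusion of patients who have previously received one day of corticosteroids during hospital stay, which was not allowed at first", a change made after 182 patients, and two or more days remains an exclusion. The term should therefore be constant or nearly so at the 96-patient look, and it adds no useful power later.

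The protocol's missing-data provision reads "Missing data on the primary outcome will be dealt with using multiple imputation techniques" and does not cover baseline covariates in the mortality model. Age and PaO₂/FiO₂ are needed for eligibility, so few values should be missing, but a rule costs one sentence.

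**Conclusion.** The point holds as a cheap improvement in efficiency. Adjusting for age and PaO₂/FiO₂ would gain about 0 to 2 points of power if they are weakly prognostic and about 1 to 6 if moderately so, with type I error unchanged near 5%. Gains of 5 to 19 points arise only with strong covariates. These figures rest on assumed control mortality of 40 to 65%, HR 0.70 to 0.80 and the covariate effects above; the documents give none of them. Confidence is medium.

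Three stronger readings are not supported:

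- A reader might infer that the mortality analysis is biased or wrong. The unadjusted test keeps its size, and its hazard ratio is a different quantity from the conditional one.
- A reader might infer that the trial falls short of a mortality power target. The plan sets none.
- A reader might infer that the change is free, or that a few missing values would cancel it. It alters the meaning of the reported hazard ratio, and with 5% missing some of the gain remains even in a complete-case analysis.

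**What to change.** Replace the mortality sentence in the SAP and in the DMC charter with wording such as:

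> Death from any cause to day 28 will be compared with a Cox model containing a centre random effect (frailty) and adjusted for age and PaO₂/FiO₂, each as a continuous term. These are the covariates named for the ordinal model. The hazard ratio is conditional on these covariates. Any missing baseline covariate will be singly imputed without using treatment allocation (for example, by the overall mean), so that every randomised patient stays in the model. The model without covariates will be reported as a sensitivity analysis.

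Prior corticosteroid use may be added at the final analysis for consistency with the primary model, but the gain does not depend on it.

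Date the change before the steering committee or trial statisticians see comparative data; the protocol gives both groups database access before publication.

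The cost is a short amendment to two documents, one imputation rule, one extra reported model, and a hazard ratio that must be labelled conditional. No new data are needed.

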	n = xxx	n = xxx	Dex. versus Cont. [IC95%]	p valor
Primary outcome				
Ventilator free days from 1 to 28 d, mean (SD)	xx.x ± xx.x	xx.x ± xx.x	x.xx [x.xx; x.xx]	x.xx
Secondary outcomes				
Clinical status at day 15, N (%)				
Category 1 - 5 versus 6 (alive vs dead)	x.xx (x.xx)	x.xx (x.xx)	x.xx [x.xx; x.xx]	x.xx
Category 1 - 4 versus 5 - 6	x.xx (x.xx)	x.xx (x.xx)	x.xx [x.xx; x.xx]	x.xx
Category 1 - 3 versus 4 - 6	x.xx (x.xx)	x.xx (x.xx)	x.xx [x.xx; x.xx]	x.xx
Category 1 - 2 versus 3 - 6	x.xx (x.xx)	x.xx (x.xx)	x.xx [x.xx; x.xx]	x.xx
Category 1 versus 2 to 6 (at home versus hospital or dead)	x.xx (x.xx)	x.xx (x.xx)	x.xx [x.xx; x.xx]	x.xx
All-cause mortality at 28 days	x.xx (x.xx)	x.xx (x.xx)	x.xx [x.xx; x.xx]	x.xx
Number of days of MV from 1 to 28 d	x.xx (x.xx)	x.xx (x.xx)	x.xx [x.xx; x.xx]	x.xx
ICU free days at 28 days	x.xx (x.xx)	x.xx (x.xx)	x.xx [x.xx; x.xx]	x.xx
SOFA scores				
48 hours	x.xx (x.xx)	x.xx (x.xx)	x.xx [x.xx; x.xx]	x.xx
72 hours	x.xx (x.xx)	x.xx (x.xx)	x.xx [x.xx; x.xx]	x.xx
7 days	x.xx (x.xx)	x.xx (x.xx)	x.xx [x.xx; x.xx]	x.xx
Adverse events				
New diagnosis of infection until day 28, N (%)	x.xx (x.xx)	x.xx (x.xx)	x.xx [x.xx; x.xx]	x.xx
Insulin use for hyperglycemia, N (%)	x.xx (x.xx)	x.xx (x.xx)	x.xx [x.xx; x.xx]	x.xx

Sensitivity analyses

We plan to perform analyses to assess treatment effects on the primary and secondary outcomes considering only patients that received the proposed treatment in the intervention group and patients that not received corticosteroids in the control group (per protocol analysis). Additionally, we will also perform sensitivity analysis for the primary outcome in the following groups:

1. Confirmed COVID-19 infection
2. Confirmed and probable COVID-19 infection
3. Patients which received corticosteroids and patients which did not received corticosteroids (as treated analysis)
4. Patients which received the proposed treatment in the intervention group and patients that not received corticosteroids in the control group (Per protocol analysis)

Subgroup analyses

Will also perform subgroup analysis adding an interaction parameter with group in the main model for (Table 3S):

1. Age, years (< 60 and ≥ 60)
2. PaO₂/FiO₂ ratio, mmHg (≤ 100 and >100)
3. SAPS3, points (< 50 and ≥ 50)
4. Duration of symptoms at randomization, days (≤ 7 and > 7)
5. Duration of moderate / severe ARDS to randomization, hours (≤ 24 hours and > 24 hours to 48 hours)
6. Position at randomization; (prone or supine)
7. HScore (≥ 169 and < 169)

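### Does the day-15 ordinal analysis need a further step because grouping categories 1 to 4 cannot repair every failure of proportional odds?

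*Combined protocol and SAP*

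**What the plan says.** The statistical methods text of the SAP (Appendix 3) gives the model: "For the clinical status of patients, an ordinal logistic regression will be used". It is "adjusted for age and PaO₂/FiO₂ ratio, with random intercepts for the center". The summary is a single number: "The results will be presented as a proportional odds ratio comparing two combinations: Intervention versus Control". If the assumption behind that number fails, the SAP has one remedy: "In case of the proportional odds assumption is not met, categories of the Ordinal scale 1-4 will be grouped as a single category".

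The same paragraph adds a second layer of results that does not depend on the assumption: "The cumulative ordinal scores will be presented separately, as well as the main secondary results", and "Each odds ratio will be estimated using mixed logistic regression". Table 2S carries this out. It has five rows for day-15 status, one per split of the scale, each with an effect, a 95% interval and a p-value. Among them are "Category 1 - 4 versus 5 - 6" and "Category 1 - 5 versus 6 (alive vs dead", the two splits that survive grouping.

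The SAP classes every secondary outcome as exploratory and sets one significance level, 0.05, for all analyses. It does not say how proportionality is judged, whether it is judged again after grouping, or how the common odds ratio ranks against the five separate ones. Table 2S as available has no row for the common odds ratio.

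**The concern.** A fallback for a failed assumption should deal with the failure that is most likely to matter. In ventilated patients that could well be a drug that gets survivors off the ventilator sooner but changes mortality little, or the reverse. Such a pattern separates the cut between levels 4 and 5 from the cut between levels 5 and 6. Grouping levels 1 to 4 leaves both cuts in place and still forces one odds ratio on them. The three-level result would then be an average of two unequal effects, reported after a step that appears to have cured the problem.

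Two silences add to this. With no criterion named, the decision to group could be made after the data are seen, in an open-label trial. With no stated ranking, an analyst could choose between the common odds ratio and any of the five separate ones. At stake is the reading of one secondary outcome that is also listed in the protocol abstract.

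**Working it through.** **Which constraints grouping removes.** Six levels have 5 cut-points, and one common odds ratio imposes 5 − 1 = 4 equality constraints. After grouping there are 3 levels and 2 cut-points, so 2 − 1 = 1 constraint remains: equal odds ratios at 4|5 and 5|6. Pooling levels 1 to 4 does not alter who lies on either side of those two cuts, so their odds ratios are the same before and after. This needs no assumption about the data.

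**Inputs for the size.** The documents give no figure for the day-15 analysis, so there is none to reproduce. The final sample size is 350 with 1:1 allocation, hence 350/2 = 175 per arm. All category shares are assumed. The fits are unadjusted, without covariates or centre effect. An odds ratio above 1 favours dexamethasone.

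**Example 1, effects differ between ventilation and death.** Levels 1 to 6: control 6/5/7/7/40/35%, dexamethasone 9/7/10/9/32/33%. With cumulative shares P at each cut, OR = [P_dex/(1 − P_dex)] / [P_con/(1 − P_con)].

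| Cut | Control P | Dex. P | OR |
|---|---|---|---|
| 1\|2 | 0.06 | 0.09 | 1.55 |
| 2\|3 | 0.11 | 0.16 | 1.54 |
| 3\|4 | 0.18 | 0.26 | 1.60 |
| 4\|5 | 0.25 | 0.35 | (0.35/0.65)/(0.25/0.75) = 1.62 |
| 5\|6 | 0.65 | 0.67 | (0.67/0.33)/(0.65/0.35) = 1.09 |

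Lack of fit is 2 × (saturated log-likelihood − proportional-odds log-likelihood) at the expected counts. It is 2.71 on six levels and 2.69 on three. The common odds ratio is 1.31 on both scales. Grouping repairs nothing here.

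With odds ratios of 1.6 to 2.0 at the first four cuts and 1.0 for death, and control shares for 1-4/5/6 from 15/45/40% to 40/35/25%, lack of fit is 2.9 to 10.2 before grouping and 2.8 to 10.1 after.

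**Example 2, effects differ only at the lower cuts.** Same control shares, odds ratios 0.8, 1.0, 1.2, 1.5, 1.5. Lack of fit is 2.81 before grouping and 0.00 after. The fallback works.

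**What the planned rows would show in example 1.** The standard error of log OR is √(sum of 1/cell count).

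- 4|5: counts 61.25 and 113.75 (dex.), 43.75 and 131.25 (control). SE = √(0.0163 + 0.0088 + 0.0229 + 0.0076) = 0.236. OR 1.62, 95% interval 1.02 to 2.56.
- 5|6: counts 117.25 and 57.75 (dex.), 113.75 and 61.25 (control). SE = √(0.0085 + 0.0173 + 0.0088 + 0.0163) = 0.226. OR 1.09, 95% interval 0.70 to 1.70.

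Both rows are reported in every case and neither assumes proportionality.

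**What a re-check after grouping would add in example 1.** Assume likelihood-ratio tests at 5%, on 4 degrees of freedom for six levels and 1 for three.

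- The six-level test fails, and grouping follows, in about 23% of trials.
- Among those trials the three-level test flags 78% to 87%, depending on the simulation run.
- End to end: 0.23 × 0.78 = 0.18 to 0.23 × 0.87 = 0.20.
- In the other 77% no grouping occurs, no re-check is run, and the six-level common odds ratio stands, which averages 1.31 as well.

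**The case for a change.** The best case for a change is this. The only remedy in the SAP misses a clinically plausible failure, and that follows from the structure of the scale. The trigger is unnamed, and it matters: in example 1 the scale would be grouped in 8%, 23% or 34% of trials at a 1%, 5% or 10% threshold. The common odds ratio can also mislead. With assumed odds ratios of 1.8 at the first four cuts and 0.8 for death, the three-level model gives 1.12 to 1.23, which hides a mortality effect in the opposite direction. A few sentences and one table row would settle all this before results are known.

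The structural point and the silence on the criterion stand. Three things weaken the call for change.

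- The reversed mortality effect would be plain in the alive-versus-dead row, and mortality at day 28 has its own model.
- The blanket 0.05 level is not tied to a proportionality test, but it is the threshold an analyst would use by default. The text also names the estimate: the proportional odds ratio, on the grouped scale if need be. A missing row in a blank table shell does not undo that.
- Naming the test, ranking the rows and adding a row would change no estimate. The one substantive addition, the re-check, is a second pre-test that chooses the reported result. It has about 38% power in example 1 even if it were run in every trial. Larger violations would be flagged more often, but they would also be more obvious in the separate rows.

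**Conclusion.** No change to the plan is needed. Grouping levels 1 to 4 is a partial remedy: it lifts three of the four constraints and leaves one, so a difference between the ventilation effect and the mortality effect passes through unaltered (common odds ratio 1.31 before and after in example 1, against 1.62 and 1.09 at the two cuts). The plan does not rely on the remedy alone, because the five separate odds ratios are reported regardless and would show the difference. The unnamed criterion and the missing row for the common odds ratio are gaps that a competent analyst fills sensibly. A re-check would catch about one trial in five in example 1.

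The structural result and the unconditional reporting are read directly from the SAP. The sizes rest on assumed category shares, unadjusted fits, 175 per arm and an assumed likelihood-ratio test, and nothing in the documents shows that the troublesome pattern will occur. The consequence is confined to one exploratory secondary outcome. The ventilator-free-days analysis and the stopping rules, which use ventilator-free days, mortality and adverse events, do not depend on it.
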